The study is designed as a prospective, multi-center, randomized, single blinded, controlled study. Patients will be enrolled at a maximum of seventeen (17) centers. Patients will be evaluated pre-operatively and at 6 weeks, 3 months, 1 year, 2 years and annually thereafter until the last patient entered into this study has completed their 2-year evaluation.

STUDY GROUPS AND TREATMENTS

Patients will be randomized to either the Comprehensive® Shoulder System with nano humeral component (investigational) or the Comprehensive® Shoulder System with mini stem component (control) group. Patients will be randomized using a 1:1 (Investigational: Control) blocked randomization plan. The treatment assignment will be revealed intraoperatively. Every attempt will be made to blind patients to their treatment until the end of the study. If a patient is revised or withdraws consent and at the request of the patient, blinding may be discontinued as no further data will be collected.

NUMBER OF PROCEDURES

A total of 264 subjects will be enrolled in this study (132 Control and 132 Investigational).

SELECTION OF SUBJECTS

All subjects considered for participation in the study will be assessed according to predetermined eligibility criteria, listed below. All subjects considered for enrollment must be

recorded on the Subject Screening Log (see Exhibit 11), including patients who are considered but not consented, consented but not randomized and consented and randomized.

Inclusion Criteria

- Patients with non-inflammatory degenerative joint disease including osteoarthritis.
- Patients where the device will be used in the correction of a functional deformity, specifically deformities that prevent congruent articulation of the glenohumeral joint. Examples include but are not limited to: humeral head structural deformity, osteophyte formation restricting range of motion, etc.
- Patients with pain and/or loss of function in the shoulder for whom other treatment modalities have been unsuccessful. Examples include but are not limited to: activity modification, physiotherapy, and anti-inflammatory or other types of medication.
- Patients requiring unilateral or staged bilateral shoulder arthroplasty

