- Patient must be anatomically and structurally suited to receive the implants. During the pre-operative templating, it must be confirmed that the humeral neck is of sufficient diameter to implant at least the smallest nano humeral component and that the humeral neck cortex is intact.
- Patients who are 21-90 years of age at the time of surgery.
- Patients who are skeletally mature
- Patients with an ASES score \leq 40.
- Patients who are willing and able to return for scheduled follow-up evaluations
- Patients who have completed a valid, IRB approved Informed Consent Form
- Patients for whom the surgeon has confirmed intraoperatively has no cyst > 1cm and not more than one cyst at the implantation site
- Patients who agree to be blinded to treatment until evaluations are completed at the 22+ month endpoint.

Exclusion Criteria

- Patients diagnosed with avascular necrosis or post-traumatic arthritis of the humeral head
- Patient presents with shoulder joint infection, sepsis, osteomyelitis or distant foci of infections which may spread to the implant site.
- Patients with cuff tear arthropathy.

- Patients who have undergone a Hemi-, Total, or Reverse Total Shoulder arthroplasty in the affected shoulder.
- Patient presents with a malunion or non-union of the tuberosities of the proximal humerus.
- Patients with osteoporosis, osteomalacia, rheumatoid arthritis, metabolic disorders of bone, muscle or connective tissue, gross deformity or any other condition of the proximal humerus (defined as severe destruction or deformity of the proximal humerus that precludes placement of the device) that in the Investigator's medical judgment could compromise implant fixation or bone healing.
- Rapid bone destruction, marked bone loss or bone resorption apparent on roentgenogram.
- Patients with neurologic or other disorders that would either affect the stability of the shoulder prosthesis, i.e., Charcot's joint, uncontrolled seizures, etc.
- Patients diagnosed with any condition that may limit their ability to complete the consent form or would affect their capability or willingness to return to the clinic for assessments and/or follow directions (i.e. mental illness).
- Bone cancer, either primary or secondary, that affects the shoulder.
- Patients presents with symptoms of chronic steroid use as defined as use of oral steroids for a chronic condition for 12 months prior to and including the date of surgery (inhaled and topical steroid usage is allowed).

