- Patients with a life expectancy of less than three years.
- Patients diagnosed with severe shoulder instability
- Patients diagnosed with subscapularis incompetence
- Patients with active medico-legal activity regarding the index shoulder
- Patients known to be pregnant, planning to get pregnant, a prisoner, and/or alcohol or drug abuser
- Patients known to be involved in worker's compensation litigations regarding index shoulder
- Patients with known metal allergy
- Patients who refuse to sign the IRB approved consent form.
- Patients who are found intraoperatively to require a specific treatment and are unable to be randomized

• Patients, found at the time of intraoperative examination to have a single cyst >1cm in size or multiple cysts at implantation site

NOTE: Patients with a previous total shoulder replacement of the contralateral shoulder are eligible for participation in the study. However, the patient and surgeon must allow for at least 9 months between procedures.

PATIENT POPULATION

A study population of 132 investigational shoulders and 132 control shoulders undergoing primary total shoulder arthroplasty for any of the diagnoses in the Inclusion Criteria will be included in this study. All patients, regardless of sex, race, or geographic location must meet all the eligibility criteria. All patients must sign an Informed Consent to be enrolled into the study. The study requires that bilateral patients must be staged so, a separate Informed Consent must be completed for each operative side.

INSTITUTIONS

A maximum of 17 investigational sites will enroll patients into the study.

DURATION OF THE STUDY

Patient recruitment is expected to take place over a period of 24 months and all patients are to be followed annually until the last patient enrolled reaches the 2-year follow-up time point. Therefore, some patients will be evaluated for 3-5 years post-operatively or longer, depending on the length of enrollment.

STUDY DEFINITIONS AND GLOSSARY OF ABBREVIATIONS

Withdrawal: Patients who die or who formally withdraw their consent (in writing) to additional follow up. Patients who have had all components removed or humeral stem components removed.

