Abbreviations:

- IRB: Institutional Review Board
- ASES: American Shoulder and Elbow Surgeons Score
- SANE: Single Assessment Numeric Evaluation
- CRF: Case Report Form

RANDOMIZATION

The randomization plan will be produced using SAS v 9.2 for Windows. The sponsor will review preoperative paperwork; Informed Consent, Historical Record, and pre-operative American Shoulder and Elbow Surgeons Score prior to enrollment in the study and approve randomization for a subject based on those criteria that are evaluated and confirmed during or prior to the pre-operative visit. Control and accountability of the humeral investigational device will be managed in accordance with Sponsor SOPs.

Randomization must not occur until the surgical procedure has commenced, and the Intraoperative assessment of inclusion/exclusion criteria is completed. Patients who have met all eligibility criteria following the intraoperative assessment, and have signed the IRB-approved informed consent will be randomly assigned to one of two treatment groups. Patients will be randomized using a 1:1 blocked randomization scheme for investigational: control devices. Bilateral patients will be randomized by shoulder. See the Statistical Analysis Plan section for a specific description of the randomization scheme.

PATIENT MANAGEMENT

Table 1 summarizes the case report forms (CRFs) required during the course of the study. All surgery and follow up case report forms are recommended to be sent to Biomet Manufacturing Corp. within 2 weeks of the patient's operative/follow-up evaluation date. All Serious Adverse Events must be sent within 24 hours of the investigator's awareness of the event.

Pre- and post-operative clinical data will be collected by trained, authorized study personnel with the exception of patient-reported outcome assessments. Exhibit 11 contains an example of the Study Signature Log that will be utilized to document authorized study personnel. Clinical and patient reported outcomes will be collected on Case Report Forms (CRFs), as summarized in Table 1. Case Report Forms or checklists/worksheets may be used as source documentation when a complete source does not otherwise exist at the site.

Table 1: Screening and Follow-Up Clinical and Radiographic Exams						
Action	Pre- Operative	Intra- Operative	6-Weeks	3-Months	1-Year	2-Years annually thereafter***
Obtain written informed consent	x					
Complete subject screening and enrollment log	x					

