Balanced, blocked randomization (1:1, Investigational: Control) will be implemented. Randomization will be per shoulder, and each shoulder will count as a separate case toward the total sample size. In the event that a screen failure occurs post-randomization, randomization will not be reassigned and this shoulder will not count toward the overall sample size. Randomization will continue with the next shoulder enrolled as previously described until the minimum sample size is reached in both treatment groups. Randomization will be blocked by site, and each site will receive separate randomization plans using a predetermined block size that will remain undisclosed to the sites.

SAMPLE SIZE CALCULATION INITIAL SAMPLE SIZE CALCULATIONS AND ASSUMPTIONS

The primary objective of this study is to show that the Investigational device is non-inferior to the Control device with respect to three co-primary endpoints at 22+ months. The sample size for each endpoint was calculated, and the largest chosen as the sample size for this study. The endpoint requiring the largest sample size was Radiographic Success; therefore the sample size for this study will be the one described immediately below. For reference, the sample size for the other two endpoints is shown as well.

Radiographic Success

Non-inferiority sample size calculations were implemented in nQuery Advisor 7.0 software using a 1:1 ratio of Investigational to Control subjects. This software uses methodology as described in a text by Farrington and Manning⁵.

The sample size needed to obtain 90% power for testing for non-inferiority of the investigational device to the control device with regard to radiographic success was calculated as follows:

⁵ Farrington and Manning. "Test statistics and sample size formulae for comparative binomial trials with null hypotheses of non-zero risk difference for non-unity relative risk". *Statistics in Medicine* 9(1990) pp 1447-1454.

Definitions:

 p_I : Proportion of Radiographic success in the Investigational treatment group

 p_C : Proportion of Radiographic success in the Control treatment group.

δ: Non-inferiority margin. Lower 95% confidence bound for difference in proportions of clinically successful subjects at 22+ months (Investigational – Control) must be greater than -δ.

For a specified constant, $0 < \delta < 1$, the hypotheses of non-inferiority are:

 $H_0: \ p_I - p_C \le -\delta \ vs. \quad H_A: \ p_I - p_C > -\delta.$

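### One fixed, undisclosed block size per site lets an unblinded surgeon guess some assignments above chance before deciding intraoperative eligibility

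*Combined protocol and SAP*

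**What the plan says.** - **Allocation (SAP, Randomization Details):** "Balanced, blocked randomization (1:1, Investigational: Control) will be implemented". "Randomization will be blocked by site, and each site will receive separate randomization plans", with a "predetermined block size that will remain undisclosed to the sites". The size is in the singular, no value is given, and varying sizes are not mentioned.
- **Blinding (Section B, Study Groups and Treatments):** "The treatment assignment will be revealed intraoperatively". The study is single-blind: "Every attempt will be made to blind patients to their treatment until the end of the study".
- **Order of events (Section B, Randomization):** "Randomization must not occur until the surgical procedure has commenced, and the Intraoperative assessment of inclusion/exclusion criteria is completed". The sponsor reviews the pre-operative paperwork before approving randomisation.
- **Intraoperative eligibility:** one criterion is measurable: "Patients for whom the surgeon has confirmed intraoperatively has no cyst > 1cm and not more than one cyst at the implantation site" (Inclusion Criteria). Another is open: "Patients who are found intraoperatively to require a specific treatment and are unable to be randomized" (Exclusion Criteria).
- **Scale (Overall Design; Number of Procedures):** 264 shoulders at no more than 17 centres.

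The documents do not say who holds the allocation list or how the next assignment is released.

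**The concern.** Randomising after the eligibility check conceals the draw itself. It does not stop a surgeon from inferring the next draw from the assignments already seen in the current block. If the next device can be guessed, an open-ended exclusion can be applied differently according to the guess, and the arms then differ before randomisation.

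The protocol supplies a plausible motive. Section C says the stemless design may raise some implant-related risks, failure of biologic fixation in particular. A surgeon expecting the stemless device could be readier to exclude doubtful bone. That would favour the investigational arm, and in a non-inferiority trial this is the anti-conservative direction. Neither patient blinding nor independent radiographic reading protects against selection before randomisation.

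Few events decide the result. Take 112 evaluable shoulders per arm and the SAP's Wald bound. With 8 control failures and 12 investigational failures, the lower bound is -0.0357 - 1.645 x 0.0380 = -0.098, which passes the -0.10 margin. With 13 investigational failures it is -0.0446 - 1.645 x 0.0388 = -0.109, which fails.

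**Working it through.** **Inputs.** Total 264 and at most 17 sites, both from Section B: 264/17 = 15.5, taken as 16 shoulders per site. The total follows from the SAP's own calculation: (1.645 + 1.282)^2 x 2 x 0.93 x 0.07 / 0.10^2 = 111.5, so 112 per arm; 112/0.85 = 131.8, so 132 per arm. The plan gives no figure for block size or predictability, so block sizes below are assumptions.

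**1. Size known or worked out.** In a 1:1 permuted block of size 2b, the expected share of assignments known with certainty is 1/(b+1). Check for a block of 4:
- The third assignment is certain with probability 1/3 and the fourth always, so (1/3 + 1)/4 = 33%.
- The best guess is right with probability 1/2, 2/3, 2/3 and 1 at the four positions, so 2.833/4 = 71%.

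| Block size | Certain | Best guess right | Certain among 264 |
|---|---|---|---|
| 2 | 50% | 75% | 132 |
| 4 | 33% | 71% | 88 |
| 6 | 25% | 68% | 66 |
| 8 | 20% | 67% | 53 |

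**2. Size fixed but unknown.** Assume that an ideal guesser sees all 16 assignments at a site and starts with sizes 2, 4, 6 and 8 equally likely. The probability that the next assignment is investigational is the sum over sizes s of w_s x (s/2 - o_s)/(s - k_s). Here k_s is the number already assigned in the current block if the size is s, o_s is how many of those were investigational, and w_s is the weight on size s, updated after each assignment. Simulating many sites gives:

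| True size | Certain | Best guess right | Guessable at 80% or better |
|---|---|---|---|
| 2 | 0% | 75% | 44% |
| 4 | 7% | 71% | 38% |
| 6 | 5% | 66% | 32% |
| 8 | 14% | 67% | 38% |

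Mean best-guess accuracy over the four sizes is (75 + 71 + 66 + 67)/4, about 70%; chance is 50%.

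**3. Randomly varying sizes.** The guesser now knows which sizes are in the mix but not their order. Same 16 shoulders per site:

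| Mix | Certain | Best guess right | Guessable at 80% or better |
|---|---|---|---|
| 4, 6, 8 | 3% | 67% | 19% |
| 4, 6 | 6% | 68% | 30% |
| 2, 4, 6 | 4% | 70% | 47% |
| 2, 4 | 10% | 72% | 55% |

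**4. Like for like.** Part of the gain from the 4/6/8 mix comes from ruling out blocks of 2. Repeating step 2 with only sizes 4, 6 and 8 as candidates gives 5-14% certain and 23-30% guessable at 80% or better, against 3% and 19% for the mix. The gain remains but is smaller.

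**The case against.** The strongest reply is that undisclosed blocking by site is an accepted design and the plan has real safeguards. Randomisation waits for the completed intraoperative assessment, and the sponsor approves it after reviewing paperwork. The cyst rule is a size and a count. Osteoporosis, marked bone loss and conditions that could compromise fixation are excluded whatever the arm. Patients consented but not randomised go on the Subject Screening Log, so selective exclusion would leave a trace. Non-disclosure also works on certainty: for a block of 4 it cuts certain assignments from 33% to about 7%. The proposed remedy barely changes average guessing accuracy.

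Most of this stands, and it limits the point. It does not remove it: best guesses remain well above 50% with an undisclosed size, and the specific-treatment exclusion stays open to judgement.

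A reader might infer four stronger claims that the documents do not support:
- **That surgeons see a site's whole sequence.** The number of surgeons per site and whether they share assignments are not stated. Step 2 assumes full sight, so it is a worst case.
- **That non-disclosure gives little protection.** It gives little against guessing but a good deal against certainty.
- **That sites hold an open list**, because each receives a separate plan. A size kept from the sites argues against that, although the release mechanism is not described.
- **That no analysis could address the bias.** The SAP compares baseline characteristics, fits covariate models and tests treatment-by-centre interaction. These might reveal a material imbalance. The named covariates include no measure of bone quality, so adjustment would be incomplete.

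**Conclusion.** The point holds as a modest, conditional weakness. On the plain reading there is one block size within each site. The text does not rule out different sizes at different sites, but that would not change the argument within a site. Some assignments can be guessed above chance before a partly subjective eligibility decision; most cannot be known.

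The 50%, 33% and 25% figures apply only if the size becomes known. With a fixed unknown size, about 0-14% are certain and 32-44% are guessable at 80% or better. These figures rest on an assumed set of block sizes, an average of 16 shoulders per site at the maximum number of sites, and a guesser who sees and uses every assignment optimally. Smaller sites, or several surgeons who do not share assignments, would lower them. Nothing in the documents shows that selective exclusion will happen or how far it would move any endpoint.

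**What to change.** For assignments not yet issued, replace the single block size with permuted blocks of randomly varying size within site. A mix of 4, 6 and 8 is suitable; blocks of 2 should be avoided, because mixes containing them raise the share of highly predictable assignments to about 47-55%. Generate and hold the lists centrally, and state in Randomization Details how each assignment is released in the operating room. Recording the reason for each intraoperative exclusion and tabulating these by site would help show whether selection occurred.

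Costs: the site plans must be reissued. An unfinished block of 8 can leave the arms at a site differing by up to 4 shoulders. Under Anticipated Changes, the amendment needs IRB approval and, if necessary, FDA approval. Sample size, endpoints and surgical procedures do not change. The benefit is mainly fewer certain and highly predictable assignments; average guessing accuracy will stay near 67%.

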Subjects who have been randomized to the Investigational or Control group in this study comprise the All Enrolled population. The co-primary endpoints will be analyzed for the All Enrolled population and the results will be compared to the primary analyses performed on the Analysis population to determine whether the results of this analysis are consistent for both populations. For patients in the All Enrolled Population who are missing data necessary for the determination of any of the co-primary endpoints at 22+ months, data will be imputed as described below in the section "Sensitivity Analyses."

ANALYSIS POPULATION

Subjects who have been randomized to the Investigational or Control group in this study and who have complete data for a primary endpoint collected per the protocol at 22+ months or who have had a revision or removal at or before 26 Months will be included in the Analysis Population. This is the population that will be used in the primary study analysis and determination of study success. Those subjects who are missing their primary endpoint at 22+ months will be included as part of the All Enrolled population described above. Subjects with protocol deviations will be analyzed on an individual basis to determine if they will be included in the Analysis Population.

MISSING DATA AND SENSITIVITY ANALYSES

Data will be considered "missing" for a given primary endpoint if this endpoint cannot be calculated or is not available for a subject in the All Enrolled population. If the subject has had a

device failure at any point on or prior to their 22+ month outcome, they will *not* be considered as missing data for the Absence of Revision/Removal/UADE endpoint, as this endpoint is cumulative. A subject who has had a revision or removal prior to two years will be considered a radiographic failure at the 22+ month time point for purposes of the primary analysis. When possible (i.e. the subject is seen by a study investigator in a non-emergency situation and collection of the data will not cause undue burden), ASES scores will be collected for these cases before the revision is performed in order to prevent these patients from missing knee scores in the primary efficacy analyses.

Sensitivity analyses will examine the sensitivity of the results to missing values of the primary outcomes using the following analyses:

Outcome Type	Analysis Description	
Binary	Tipping Point Analysis: Missing observations are replaced with	

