(Radiographic Success,	values until the lower limit of the 95% Confidence interval for the	
Absence of	difference in proportions is equal to the non-inferiority margin	
Revision/Removal))	(the tipping point). Graph will show which imputations of	
Kevision/Kemovaljj	success/failure for the missing values in the investigational and	
	control groups lead to a conclusion of inferiority, and which lead	
	to a conclusion of non-inferiority. Missing Values as Success: Imputation of missing values as	
	"success"	
	Missing Values as Failures: Imputation of missing values as	
	"failure"	
	lanure	
	Last Observation Carried Forward: Missing observations in	
	either group are imputed by taking the most recent outcome prior	
	to 24 months and using it in place of the missing 24-month	
	outcome.	
	2 Year In-Window Analysis : Only data collected within the 2-	
	year per-protocol visit window (22-26 months) are included in	
	this analysis.	
	Multiple Imputation: This method replaces each missing value	
	with a set of plausible values that represent the variability around	
	the choice of which value to impute.	
Continuous	Replace with Maximum: Imputation of missing ASES as "100"	
(ASES Score)		
	Replace with Minimum: Imputation of missing ASES as "0"	
	Last Observation Carried Forward: Missing observations in	
	either group are imputed by taking the most recent outcome prior	
	to 24 months and using it in place of the missing 24-month	
	outcome.	
	2 Year In-Window Analysis : Only data collected within the 2-	
	year per-protocol visit window (22-26 months) are included in	

this analysis.
Multiple Imputation: This method replaces each missing value
with a set of plausible values that represent the variability around
the choice of which value to impute.

In addition, in the event that one or more subjects receive the opposite treatment than the one they were randomized to receive, a sensitivity analysis will be done on patients "as randomized" to make sure it is consistent with the primary analysis ("as treated"). However, because randomization will be performed intra-operatively and the patient must be able to receive either treatment in order to be randomized, this situation is not expected to occur. Other sensitivity analyses will be conducted as needed (i.e. if the effect of missing data on a particular primary outcome is still unclear).

TESTS FOR INTERACTION

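### The ASES test that decides success drops shoulders lost before 22+ months although their earlier scores are collected, so it is exposed to outcome-related dropout that differs between arms

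*Combined protocol and SAP*

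**What the plan says.** Study Populations, Analysis Population, admits randomized subjects with complete data for a primary endpoint at 22+ months, "or who have had a revision or removal at or before 26 Months will be included in the Analysis Population". It then states: "This is the population that will be used in the primary study analysis and determination of study success". Subjects without the endpoint go to the All Enrolled Population, where missing values are imputed. The use made of that analysis is a check of agreement: "the results will be compared to the primary analyses performed on the Analysis population to determine whether the results of this analysis are consistent".

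Missing Data and Sensitivity Analyses retains device failures on the binary endpoints. "A subject who has had a revision or removal prior to two years will be considered a radiographic failure", and a device failure is never missing on the revision/removal/UADE endpoint, "as this endpoint is cumulative". For ASES the protection is weaker: "ASES scores will be collected for these cases before the revision is performed", but only when this is feasible.

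The imputation methods are introduced as follows: "Sensitivity analyses will examine the sensitivity of the results to missing values of the primary outcomes using the following analyses". For ASES the list has replacement by 100, replacement by 0, last observation carried forward, an in-window analysis, and "Multiple Imputation: This method replaces each missing value" with a set of plausible values.

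Efficacy Evaluations, Primary Endpoint, defines the deciding ASES test as a two-sample difference in means with a normal-theory bound. It uses no earlier score. Table 1 of the protocol (Screening and Follow-Up Clinical and Radiographic Exams) schedules ASES pre-operatively, at 6 weeks, 3 months and 1 year, and from 2 years on.

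**The concern.** A shoulder with a 1-year ASES score and no 22+ month score carries information about where it was heading. The deciding test discards that information, and the analysis that would use it has only a supporting role.

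This matters more in a non-inferiority trial than in a superiority trial. If poorly performing nano shoulders are lost preferentially, the observed difference moves toward zero and the bound moves away from the margin, so the loss helps the trial succeed. The stated 5% error of the ASES test would then not hold.

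**Working it through.** **The plan's own figures.** ASES sample size per arm, with SD 19, margin 9.5, one-sided 0.05 and power 90%: n = 2(1.645 + 1.282)² × 19²/9.5² = 68.5, so 69 by the normal formula and 70 with the t distribution, as stated. Attrition: 70/0.85 = 82.4, giving 83. The radiographic endpoint sets the trial size: 112/0.85 = 131.8, giving 132 per arm. The plan thus allows for 132 − 112 = 20 lost per arm.

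**The deciding test at planned attrition.** SE = 19 × √(2/112) = 2.54. The bound is the observed difference minus 1.645 × 2.54 = 4.18, so the test passes when the observed difference is at least −9.5 + 4.18 = −5.32. If the true difference is −9.5 and dropout adds a bias b, the pass rate is approximately Φ(b/2.54 − 1.645). For b = 0 this is 5%.

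**Simulation of b.** From the documents: 132 per arm, 20 lost per arm, SD 19, margin 9.5. Assumed, because the documents do not give them: 1-year and 2-year ASES bivariate normal with correlation 0.6; true difference −9.5 at both visits; chance of loss proportional to exp(−s·z), where z is the 1-year score standardised on the control mean, with s = 0.5, 1 or 2. In the nano arm these values of s put lost shoulders about 10, 18 and 28 points below retained ones at 1 year. The comparator regresses the 2-year score on the 1-year score within each arm and averages over all 132 shoulders. There were 10,000 trials per cell, so the simulation error is about 0.3 percentage points at a 10% rate.

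| Who is lost selectively | s = 0.5: bias, error | s = 1: bias, error | s = 2: bias, error |
|---|---|---|---|
| Nano only, control at random | +0.9, 10% | +1.7, 16% | +2.5, 27% |
| Nano at s, control at s/2 | +0.5, 7% | +0.8, 10% | +0.9, 10% |
| Both arms at s | 0, 5% | 0, 6% | 0, 5% |
| Control only, nano at random | −0.9, 2% | −1.7, 1% | −2.5, 0.5% |

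The comparator gave about 5% in all twelve cells. Repeat runs moved the entries by about a point (nano only: 9–10%, 16–17%, 26–27%). As a hand check, b = 1.7 gives Φ(0.67 − 1.645) = 16% and b = 2.5 gives Φ(0.98 − 1.645) = 25%.

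**Other assumptions, nano-only loss.** Correlation 0.4 gives 8–16% and correlation 0.8 gives 12–40%. At correlation 0.6, 10 lost per arm gives about 7% (s = 0.5) and 10% (s = 1); 5 lost per arm gives about 6.5% and 7%.

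**Precision under random loss.** Using the 1-year score at correlation 0.6 gives an effective size of 1/(0.64/112 + 0.36/132) = 118 per arm instead of 112.

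**How far dropouts must differ to reverse a pass.** With all 132 outcomes known, the limit is −9.5 + 1.645 × 19 × √(2/132) = −5.65. If retained shoulders show no difference, lost nano shoulders must average 5.65/(20/132) = 37 points below lost controls. If retained shoulders differ by −5, the figure is (5.65 − 5 × 112/132)/(20/132) = 9 points.

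**The case against.** Several points on the other side stand.

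- A reader might infer that success is decided on completers only. It is not. Revised and removed shoulders are included and count as failures on the binary endpoints under the stated rules, and a pre-revision ASES is sought for them. For ASES this protects only where that score is obtained.
- A reader might infer that any outcome-related dropout biases the test. It does not: with the same selection in both arms the bias is zero and the error stays near 5%. The condition is a difference between arms.
- The 9–27% range assumes that only nano loss depends on outcome. The documents do not predict that. Patients are to be blinded until the end of the study, which makes arm-specific loss less likely. Against this, Section C says the stemless design may raise the risk of loosening or migration, so the asymmetry is possible. The reverse asymmetry makes the test conservative.
- Twenty lost per arm is a planning allowance. The 2+ Year window (beyond 791 days), annual follow-up and continued contact attempts should recover some missed 2-year visits.
- The plan would display much of the effect of dropout, by multiple imputation and extreme-value replacement for ASES and by a tipping-point analysis for the binary endpoints. It remains true that the deciding ASES test does not use the earlier scores.

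A reader might also want the binary endpoints to pass a second, imputed bound. That would add a pass/fail hurdle to the endpoint that sets the sample size, at a power cost nobody has quantified. It is not part of this point.

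**Conclusion.** The point holds for ASES. The deciding test discards scores the trial collects, and its 5% error depends on outcome-related dropout being alike in the two arms. Under the stated assumptions (20 lost per arm, correlation 0.6, true difference at the margin) the error runs from under 3% to about 27% according to which arm loses its poor performers, while an analysis using the 1-year score stays near 5% in every pattern examined.

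These figures show sensitivity; they do not forecast the trial's error rate. The correlation and selection strengths are not in the documents. The comparator holds 5% here because loss was made to depend only on the 1-year score; loss driven by unrecorded deterioration after that visit would not be fully corrected. If the two devices give similar ASES results, dropout is very unlikely to change the conclusion. The exposure is greatest when the observed difference lies near −5.

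**What to change.** In Analysis Population and in Efficacy Evaluations, Primary Endpoint, make the deciding ASES test a repeated-measures model, or multiple imputation done separately by arm, using the pre-operative, 6-week, 3-month and 1-year scores. Keep the 9.5-point margin and the one-sided 95% bound. Keep the observed-data difference in means as a sensitivity analysis.

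Define the population as all randomized shoulders that received a study device. The All Enrolled Population as written is everyone randomized. It would require imputed scores for shoulders that never received a device, which the protocol elsewhere treats as screen failures, replaces, and does not count toward the sample size.

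State how deaths, and revised shoulders without a pre-revision score, enter the model. Leave the binary endpoints' tipping-point and imputation analyses as sensitivity analyses.

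The cost is a SAP amendment with a fully specified model; no patients, visits or forms are added. The trial would then rely on a missing-at-random assumption for its ASES conclusion, and the bound may be slightly less favourable if dropouts did worse. If loss is random, precision improves slightly.
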